PROTOCOL TITLE:

Efficacy and mechanistic of repeated transcranial magnetic stimulation in children with autism spectrum disorder: an open-label clinical trial

NCT NUMBER: *05472870*

PRINCIPAL INVESTIGATOR:

[name]

Xinhua Hospital affiliated to Shanghai Jiao Tong University

School of Medicine, Chief Physician

[contact]

[name]

Shanghai Mental Health Center, Professor

[contact]

VERSION NUMBER: Version 2.0

VERSION DATE: April 2, 2022

STUDY SUMMARY

Study Title	Efficiency and machanisms of rangeted transgrapial magnetic						
Study Title	Efficacy and mechanisms of repeated transcranial magnetic						
	stimulation in children with autism spectrum disorder: an open-label clinical trial						
D: Ol: /							
Primary Objective	Preliminarily explore whether accelerated continuous theta-burst						
	stimulation (a-cTBS) over left primary motor cortex (M1) can						
	improve clinical symptoms of children with autism spectrum disorder (ASD) in China.						
Secondary Objective	Explore the appropriate intervention model, effective adaptation						
	population and underlying neurological mechanisms of repeated						
	transcranial magnetic stimulation (rTMS) for ASD children.						
Sample Size	≥30 individuals						
Trial Design	This study is a single-arm open-label clinical trial, designed to						
	enroll at least 30 children with ASD aged over 4 years old.						
	The children seen in our outpatient clinics, who meet the						
	DSM-5 ASD diagnostic criteria with ADOS and strict						
	inclusion/exclusion criteria, can be enrolled for the intervention						
	after informed consent.						
	During the trial, participants will receive accelerated						
	continuous theta-burst stimulation (a-cTBS)on the left primary						
	motor cortex (M1) for 5 consecutive days and complete clinical						
	assessments within 2 weeks before the cTBS intervention						
	(pre-cTBS), repeated within 3 days after the completion of the						
	cTBS course (post-cTBS) and 1 month following the last cTBS						
	session (one month follow-up), respectively.						
Outcome measures	The primary outcome measure is the parent-reported Social						
	Responsiveness Scale (SRS) score at pre-intervention,						
	immediately after the 5 days of intervention and 4 weeks after						
	5 days of intervention.						
	Secondary outcome measures are Childhood Autism Rating						
	Scale (CARS); Repetitive Behaviors Scale-Revised (RBS-R);						
	Conners parent symptom questionnaire (PSQ), Behavior Rating						
	Inventory of Executive Function(BRIEF), Peabody Picture						
	Vocabulary Test (PPVT); Chinese Communication Development						
	Inventory (CCDI); Clinical Efficacy Rating Scale (CGI) scores.						
	Exploratory indicators are changes in resting-state						
	Electroencephalogram (EEG) characteristics before and after the						
	intervention, and Multilingual Assessment Instrument for						
	Narratives (MAIN) scores.						
Safety Evaluation	During the intervention and follow-up periods, a careful						
	physical examination will be conducted by clinician when						
	participants come to the hospital. Meanwhile, A semi-structured						

Efficacy and mechanistic of repeated transcranial magnetic stimulation in children with autism spectrum disorder: an open-label clinical trial. NCT05472870

Version: 2.0/April 2, 2022

	interview will be administered following each treatment session						
	and follow-up by the rTMS technician, special attention will be						
	paid to TMS common discomforts, such as spasms, convulsions,						
	scalp discomfort, local pain, headache, dizziness, tinnitus,						
	nausea, etc. If any adverse events or physical discomfort were						
	reported, detailed descriptions were recorded and graded						
	according to their severity.						
Inclusion criteria	A. Children aged ≥4 years old						
	B. Meet the diagnostic criteria for ASD of the DSM-5						
	C. ASD Diagnosis confirmed by the Autism Diagnostic						
	Observation Schedule (ADOS) or Autism						
	Diagnostic Interview, Revised (ADI-R)						
	D. Provide written informed consents						
Exclusion criteria	A. With metal implants in the body						
	B. History of epilepsy or other neurological disease						
	C. Require surgical treatment due to structural						
	abnormalities indicated by brain MRI						
	D. With genetic or chromosomal abnormalities						
	E. With psychiatric/mental disorder (e.g., very						
	early-onset schizophrenia) other than ASD						
	F. Suffer from serious heart disease and/or severe						
	hearing impairment						
	G. Intracranial hypertension						
	H. Participating in other clinical trials						
	I. Participants who received other interventions within						
	4 weeks prior to enrollment.						
Intervention	Participants will receive cTBS over the left M1 for 5 consecutive						
	days. The detailed parameters as follows: 80% of RMT, 60 cycles						
	of 10 bursts of three pulses at 50 Hz were delivered in 2-second						
	trains (5 Hz) with no intertrain interval (i.e. triplet standard cTBS,						
	1800 pulses, 120s). Stimulation sessions were delivered hourly,						
	10 sessions were applied per day (18,000 pulses/day).						
Research time	Expect to recruit at least 30 ASD children from May 2022 to						
	December 2023. A total of approximately 5 weeks per subject						
	will spend to complete a baseline assessment, a 5-day						
	intervention, and a 4-week follow-up after the intervention.						
	The state of the s						

ABBREVIATIONS/DEFINITIONS

ASD	Autism spectrum disorder
ADOS	Autism Diagnostic Observation Schedule
ADI-R	Autism Diagnostic Interview, Revised (ADI-R)
AE	Adverse Events
a-cTBS	Accelerated continuous theta-burst stimulation
BRIEF	Behavior Rating Inventory of Executive Function
CCDI	Chinese Communication Development Inventory
CGI	Clinical Efficacy Rating Scale
cTBS	Continuous theta-burst stimulation
DSM-5	Diagnostic and Statistical Manual of Mental Disorders 5th Edition
EEG	Electroencephalogram
M1	Primary motor cortex
MAIN	Multilingual Assessment Instrument for Narratives
PSQ	Conners parent symptom questionnaire
PPVT	Peabody Picture Vocabulary Test
RBS-R	Repetitive Behaviors Scale-Revised
rTMS	Repeated transcranial magnetic stimulation
SRS	Social Responsiveness Scale
SAE	Serious Adverse Events
TMS	Transcranial magnetic stimulation

Catalogue

1.0	Background	- 5
2.0	Objectives	
3.0	Study design	
	Appendix: study design flow	- 9
4.0	Study subjects	
4.	1 Indications	10
4.	2 Sample size and calculation method	10
4.	3 Inclusion criteria	10
4.	4 Exclusion criteria	-10
4.:	5 Exit criteria	-11
4.	6 Case rejection criteria	11
5.0	Intervention	-11
5.	1 Intervention program	-11
	2 Combined treatment	
6.0	Follow-up plan	12
6.	1 Follow-up time arrangement	-12
	2 Follow-up content: Process schedule	
7.0	Outcome measures	-12
7.	1 Primary outcome measures	-12
7.	2 Secondary outcome measures	-13
7.	3 Exploratory outcome measures	- 14
8.0	Safety evaluation	14
8.	1 Physical Signs	14
8.	2 Adverse events incidence	-14
9.0	Adverse events and serious adverse events	-14
	1 Definition of adverse events	
9.	2 Record of adverse events	- 14
9.	3 Serious Adverse Events	- 15
10.0	Ethical Committee and informed consent	-15
10	0.1 Ethical Committee	-15
10	0.2 Informed consent	15
11.0	Data management and statistical analysis	-15
11	.1 Data Collection	
11	.2 Data Monitoring and Auditing	-16

1.0 Background

Autism spectrum disorder (ASD), also known as childhood autism, was first reported and named by American psychiatrist Kanner in 1943. It is a neurodevelopmental condition with a specific combination of impairments in social communication and repetitive behaviors, highly restricted interests and/or sensory behavior, beginning early in life. In recent years, the global incidence of autism in children has been rising sharply, affecting approximately 1/100 children around the world and more in some countries and districts [1]. Moreover, a significant proportion of ASD children have a combination of different degrees of intellectual impairment, who need more attention and care, bringing heavy burden to families and society [2].

Currently, it is believed that individualized precise treatment based on etiology is the most recommended way to treat neuropsychiatric diseases including ASD[3]. However, ASD is thought to be the result of a combination of many factors acting on the nervous system, including the individual's genetic background, adverse environment, so there is a significant heterogeneity on the behavioral symptoms and severity phenotype of children with ASD, which further increases the difficulty of diagnosis and treatment. So far, there are few highly evidence-based and effective treatment for ASD worldwide[4], especially for core social communication symptom, and children's treatment is still based on symptomatic behavioral intervention, such as behavioral analysis therapy (ABA), Denver early intervention mode, etc. Many families cannot afford or do not have access to professional intervention, and only small-to-medium effects of improvement have been achieved despite some children received timely high-intensity interventions. Therefore, it is imperative to find new treatments that are safe, tolerable, fast acting, durable, and effective.

Repetitive transcranial magnetic stimulation (rTMS), a non-invasive neuromodulation technology, has been proposed as potential therapeutic options for the modification of the pathological neuroplasticity involved in neuropsychiatric disorders including ASD[5], and the use of rTMS in patients is relatively well tolerated and safe [6,7]. Consistant Theta-burst stimulation (cTBS) is a more efficient form of rTMS that produces stronger brain plasticity changes through lower overall stimulation intensity and shorter stimulation duration[8]. To date, There are many rTMS studies on dorsolateral prefrontal cortex (DLPFC), which found that the intervention group improved in social interaction, cognitive and executive function, repetitive and stereotyped behavior to varying degrees, and had good clinical benefits in ASD [9-13]. We noticed the primary motor cortex (M1) might be a potential stimulation target for two reasons: 1) atypical neuroplasticity was observed in M1 in autistic individuals using TMS[14,15]; 2)M1 is highly involved in the processing of

action execution[16] and emotion evaluation[17-18]. However, there has been no clinical trial targeting M1 examined the efficacy of improving ASD symptoms.

Given the scarcity of studies on rTMS stimulation over M1 and the lack of trials examining its efficacy, especially in social communication impairment, we design this single-arm open-label trial to investigate the efficacy and safety of an accelerated and high-dose continuous Theta-burst stimulation (a-cTBS) targeting left M1 for autistic core deficits in ASD children. Before drafting this protocol, our group has included 20 high-functioning ASD children aged 6-10 years old to receive cTBS on M1 in 10 consecutive days [NCT05238298], the results suggested that more than half of the children had improvement in social and language function, meanwhile, it was safe and well tolerated. The above research experience provide a guarantee for the implementation of this trial.

References

During the trial, participants will receive accelerated continuous theta-burst stimulation (a-cTBS)on the left primary motor cortex (M1) for 5 consecutive days and complete clinical assessments from the baseline to 1 month following the last cTBS session (Pre-intervention, Post-intervention and one month follow-up, respectively).

The detailed a-cTBS parameters as follows: 80% of RMT, 60 cycles of 10 bursts of three pulses at 50 Hz were delivered in 2-second trains (5 Hz) with no intertrain interval (i.e. triplet standard cTBS, 1800 pulses, 120s). Stimulation sessions were delivered hourly, 10 sessions were applied per day (18,000 pulses/day).

Efficacy and mechanistic of repeated transcranial magnetic stimulation in children with autism spectrum disorder: an open-label clinical trial. NCT05472870 Version: 2.0/April 2, 2022

Attached: Study design Flow

[figure not shown]

Figure 1. Study flow

4.0 Study subjects

4.1 Indications

Children with ASD.

4.2 Sample size and calculation method

This study will recruit at least 30 ASD children aged over 4 years old at one trial center.

Sample size calculation method:

This study is a single-arm, open-label clinical trail and most of previous rTMS studies included 10-20 ASD patient and found their symptoms had improved after rTMS intervention. For example, Wang, et al. reported the improvement of language and social symptoms in 13 children aged 3-12 years with ASD after 15 days (15 rTMS sessions in total) [Wang, et al., Frontiers in Psychiatry 2019], Fahnestock, et al. found a reduction of the disease severity among 16 children with ASD (mean age: 9 years old) after one-month rTMS intervention (20 sessions in total) [Fahnestock, et al., Drug Development Research 2021].

A minimum total sample size was estimated using G*Power, being powered (80% power and two-sided 5% significance) to detect a moderate (0.5)-to-large (0.8) standardized effect of treatment. The estimated effect size was guided by existing study results on social behavior deficits (Ni HC, et al., Autism, 2021, Barahona-Correa et al., Front Integr Neurosci, 2018). Considering the 10 % dropout rate and the fact that this study would include both low-function and high-function ASD children (further stratified analysis is required), the final sample size of this study is estimated to be at least 30.

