11.3 Selection of statistical analysis data

Statistical analysis of data from subjects who completed the full 5-day intervention and follow-up assessments (mainly for primary outcome measure, i.e., SRS).

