11.5 Statistical analysis method

Data will be preprocessed and/or analyzed using SPSS25.0, SAS9.2, Matlab, and R.

• Analysis of the primary outcome measures:

SRS scores at baseline, immediately after the end of 5-day intervention and 4 weeks after the end of 5-day intervention will be analyzed using repeated measures ANOVA.

2 Analysis of other behavioral outcome measures:

RBS-R, BRIEF, PSQ scores at baseline, immediately after the end of 5-day intervention, and 4 weeks after the end of 5-day intervention will be analyzed using repeated measures ANOVA or Friedman test.

CARS, PPVT, CCDI, MAIN scores at baseline and 4 weeks after the end of 5-day intervention will be analyzed using paired-samples t-tests or Mann-Whitney Wilcoxon test.

3 EEG analysis

EEG data will be preprocessed and analysed by MATLAB. Changes in the electrophysiologicalactivity characteristics of the brain at baseline, immediately after the end of 5-day intervention and 4 weeks after the end of 5-day intervention will be analyzed and then correlated with clinical behavioral outcome.

4 Safety evaluation

Summarize the occurrence of adverse events: summarize the number of cases,

Efficacy and mechanistic of repeated transcranial magnetic stimulation in children with autism spectrum disorder: an open-label clinical trial. NCT05472870

Version: 2.0/April 2, 2022

instances, and incidence of adverse events and list all adverse events, those related to the study intervention protocol, serious adverse events, and those leading to exit; list the number of cases, instances, and incidence of mild, moderate, and serious adverse events; give a description for adverse events related to the intervention.

SAnalysis of baseline characteristics

The analysis of baseline characteristics included: demographics (age and gender); baseline analysis of each observation used in this study.

The number of cases, mean, standard deviation, median, minimum and maximum values were calculated when the variables were quantitative indicators; the number of cases and composition ratio were calculated when the variables were categorical indicators.

12. 0 Principal Investigator and contact person

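### The 80% power stated in section 4.2 is not reached at its lower end (0.5) on the most direct reading: 27 completers give about 71%, and 80% starts at about 0.56 SD of change

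*Combined protocol and SAP*

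**What the plan says.** Section 4.2 bases the sample size partly on small earlier studies and partly on a formal calculation done in G*Power. On the calculation it makes these statements:

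- The power claim: "being powered (80% power and two-sided 5% significance) to detect a moderate (0.5)-to-large (0.8) standardized effect of treatment".
- The source of the effect, for which two works are cited: "The estimated effect size was guided by existing study results on social behavior deficits".
- The allowance for losses: "Considering the 10 % dropout rate". A planned stratified look at low- and high-functioning children is mentioned alongside it.
- The result: "the final sample size of this study is estimated to be at least 30".

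It does not name the test, the single effect used for planning, the SD that standardizes the effect, the correlation between visits, or the N before dropout.

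Two other sections fix what the calculation has to serve. Section 11.3 restricts the analysis to "data from subjects who completed the full 5-day intervention and follow-up assessments". Section 11.5 commits the primary outcome, SRS, to a three-visit analysis; after naming the baseline visit, its sentence runs: "immediately after the end of 5-day intervention and 4 weeks after the end of 5-day intervention will be analyzed using repeated measures ANOVA". The study summary presents the primary objective as exploratory, opening with "Preliminarily explore whether accelerated continuous theta-burst".

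**The concern.** A claim of 80% power over a range that starts at 0.5 is naturally read as holding at 0.5. With one arm and a two-sided 5% level, the simplest calculation matching that wording is a paired comparison with the effect in SDs of change. On that calculation 30 enrolled is too few for 0.5 and far more than 0.8 needs.

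The stake is how a result is read. SRS is the primary outcome. If its change is not significant, someone relying on section 4.2 could conclude that a moderate effect had an 80% chance of being detected and was probably absent. The real chance may have been nearer 71%, or lower under the planned ANOVA.

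**Working it through.** **Inputs stated in the plan.** Power 80%, two-sided 5%, effect 0.5 to 0.8, dropout 10%, at least 30 enrolled (4.2); completers analysed (11.3); three SRS visits, repeated measures ANOVA (11.5). Completers at the floor: 30 × 0.9 = 27.

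**Inputs assumed here.** The standardizer, the between-visit correlation ρ, sphericity and the time pattern. The plan gives none of them.

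**1. Trying to reproduce 30 (two-sided paired t, effect d in SDs of change).** Power comes from the noncentral t with n − 1 df and noncentrality d√n.

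- d = 0.5: 33 completers give 79.5%, so 34 are needed; 34 / 0.9 = 37.8, so 38 enrolled.
- d = 0.8: 15 completers are needed; 15 / 0.9 = 16.7, so 17 enrolled.

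Neither end gives 30.

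**2. Power at the stated size (same test).**

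| Completers | d | d√n | Power |
|---|---|---|---|
| 27 | 0.5 | 2.60 | 70.6% |
| 30 (no dropout) | 0.5 | 2.74 | 75.4% |
| 27 | 0.56 | 2.91 | 80.0% |
| 27 | 0.8 | 4.16 | 97.9% |

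Dropout alone does not explain the gap, since 30 completers still fall short at 0.5.

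**3. One-sided version.** At d = 0.5 and one-sided 5%, 26 completers give 79.8% and 27 give 81.2%. So 27 are needed, and 27 / 0.9 = 30 exactly. This reproduces the plan's figure but contradicts its two-sided level.

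**4. Planned analysis (one-group repeated measures ANOVA, three visits).** Under compound symmetry λ = nΣ(μ − μ̄)² / [σ²(1 − ρ)], and the SD of change squared is 2σ²(1 − ρ). With changes δ in SDs of change, ρ cancels: λ = 2nΣ(δ − δ̄)², with 2 and 2(n − 1) df. Take 0.5 as the largest change among the visits and n = 27:

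- Linear build-up (0, 0.25, 0.5): Σ = 0.125, λ = 6.75, power 61.2%.
- Full change at both later visits (0, 0.5, 0.5): Σ = 0.1667, λ = 9.0, power 74.5%. A transient change (0, 0.5, 0) gives the same.

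These are the extremes when the other post-baseline visit's change lies between zero and the maximum. Power reaches 80% at 0.533 (full change at both visits) to 0.615 (linear). At 0.8 it is 99.1% and 96.0%. If sphericity fails (ε = 0.75, assumed), power at 0.5 is 52.6% to 65.3%.

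**5. If 0.5 is in SDs of the score.** Then d in SDs of change is 0.5 / √[2(1 − ρ)]. Setting this to the 80% thresholds above gives the ρ required:

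- ANOVA, full change at both visits: ρ about 0.56.
- Paired t: ρ about 0.60.
- ANOVA, linear: ρ about 0.67.

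**6. Other routes to about 80% or to 30.**

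- Cohen's f = 0.25 with ρ = 0.5, three visits: λ = 0.25² × 27 × 3 / 0.5 = 10.1, power 79.6%. Neither value is stated, and over three visits f = 0.25 is a maximum change of 0.25/√(2/9) = 0.53 to 0.25/√(1/6) = 0.61 score SD, not 0.5.
- 0.5 taken directly as f: 98% even at ρ = 0, but only 15 completers would be needed, and it sits poorly with the label moderate.
- d = 0.8 in each of two equal functioning groups: 15 per group, 30 in all, but with nothing left for dropout. With 27 completers the groups are 13 and 14, with power 75.4% and 79.0%. Section 4.2 states neither equal groups nor powering per group.

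**The case against.** The strongest reply is that no stated number contradicts another: the shortfall appears only once 0.5 is taken in SDs of change, which section 4.2 does not say. Three parts of this stand.

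- The standardizer decides the answer. In score SDs with an assumed ρ of 0.7, power at 0.5 is 89.8% (paired t) or 83.9% to 93.1% (ANOVA). The three ratings span only about five weeks, but the documents give no ρ, so the matter cannot be settled from them. The metric used in the two cited works is not available either.
- Section 4.2 gives a range, not a single value. A planning effect of 0.56 lies inside it and gives 80.0% at 27 completers with a two-sided test, in conflict with nothing stated. By paired t, power is at least 80% over (0.8 − 0.56) / (0.8 − 0.5) = 80% of the range.
- The 61% figure is a worst case. It needs the omnibus ANOVA and exactly linear build-up. The paired comparison fits the two-sided wording better, and there the gap is about 9 points.

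What does not stand is that this is only missing detail. The text attaches 80% to a range beginning at 0.5. Every route found to 80% at that lower end adds an input section 4.2 does not give, or drops one it does.

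A reader might go further and infer that the trial is underpowered, that 30 is wrong, or that a one-sided test was run by mistake. The documents support none of these. The one-sided match to 30 is exact, but other inputs come close, and nothing shows which was used. The size is a floor, the aim is preliminary, small-study precedent also supports it, and no decision rule uses the power figure.

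**Conclusion.** The concern holds in a limited form. On a two-sided paired comparison with the effect in SDs of change, the stated 80% is met at 0.8 (about 98%) and from about 0.56 upward, but not at 0.5, where it is about 71% with 27 completers and about 75% if all 30 complete. The planned ANOVA gives about 61% to 74% at 0.5 under sphericity.

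The conclusion rests on the SD-of-change reading and on exactly 30 being enrolled with 10% lost. A score-SD reading with ρ of about 0.56 to 0.67 or more, depending on the test and time pattern, would remove the shortfall. The finding concerns the wording of the power claim, not the choice of N. Severity: minor.

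**What to change.** In section 4.2, do one of the following.

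- **Restate the claim.** For example: with at least 30 enrolled and 27 evaluable after 10% dropout, a two-sided 5% paired comparison has about 80% power at an effect of about 0.56 SD of change and about 71% at 0.5; the three-visit repeated measures ANOVA, assuming sphericity, has 80% power at a maximum change of about 0.53 to 0.62 SD of change, depending on the time pattern, and about 61% to 74% at 0.5.
- **Or document the calculation.** State the test, its sidedness, the planning effect, its standardizer, the between-visit correlation (and the sphericity value if used) and the N before dropout, if together these give 80% at 0.5.

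The second route is preferable if the sponsor still has the G*Power inputs, because it does not put assumed values into the protocol. Either takes two or three sentences. N, visits and planned analysis do not change. The only cost is that the stated power at the lower end may look slightly less favourable.
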